3.6.5 RSV resistance monitoring

Nasal samples collected from subjects with RT-PCR confirmed RSV will be subtyped, genotyped, and evaluated by genotypic and phenotypic resistance analyses. Genotypic analyses will report amino acid changes in the mature RSV F protein sequence compared to contemporary reference strains. Phenotypic analyses will report changes in susceptibility of engineered recombinant RSV variants to MEDI8897 and palivizumab neutralization compared to laboratory-derived reference viruses. A detailed description of subjects/samples to be analyzed, sample collection and testing workflow, performance characteristics of assays and methodologies, analysis plans, and reporting plans have been included in a separate clinical virology analysis plan. The details of genotypic and phenotypic analyses and presentation of these data will be included in a separate virology study report.

3.6.6 Incidence of medically attended LRTI from Day 152 to Day 361 for Season 1 and Season 2

For each season, the summaries will be provided using subjects from the respective ITT population who remained in the study at the Day 151 visit. For subjects with multiple medically attended RSV LRTI events after Day 151, only the first occurrence will be used in the summary. More specifically:

• Season 1: The incidence of medically attended RSV LRTI that occurred > 150 days (from Day 152 to Day 361) post 1st dose will be based on RSV test results (performed centrally via RT-PCR) and objective clinical LRTI criteria and will be summarized by treatment group. This endpoint will be further summarized by RSV subtype (RSV A, RSV B) and by treatment group. In addition, AEs associated with this endpoint will be summarized overall, as well as categorized by MedDRA SOC and PT. These summaries will also be provided for each cohort (pre-term, CHD/CLD).

• Season 2: Similar summaries described above for Season 1 will be provided for Season 2 and will focus on the CHD/CLD subjects in the following groups: palivizumab/palivizumab, palivizumab/MEDI8897, and MEDI8897/MEDI8897. who have been randomized to palivizumab group in Season 1 and enrolled (re-randomized) in Season 2 in either palivizumab or MEDI8897 groups. Summaries for CHD/CLD subjects who have been randomized to MEDI8897 group in both Season 1 and Season 2 will also be provided.

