This study will also summarize efficacy of MEDI8897 and palivizumab in terms of incidence of RSV LRTI. Respiratory syncytial virus results in a significant burden of disease consisting of hospitalization, visits to the emergency room (ER), and visits to outpatient clinics. This endpoint is designed to allow the capture of this total burden of disease. A separate endpoint of RSV hospitalization will also be evaluated. Because of the reduced incidence of RSV disease in this population following the introduction of palivizumab, a superiority or non-inferiority design (with RRR of MEDI8897 over palivizumab as the endpoint) is not practical. This Phase 2/3 study is designed to confirm the safety and PK while incidence of RSV LRTI (and RSV hospitalization) will be summarized and no formal statistical test will be conducted. It is anticipated that efficacy from the Phase 2b and Phase 3 studies in preterm and term infants will be predictive of efficacy in the palivizumab population.

Exploratory endpoints will examine magnitude of healthcare resource utilization (HRU) and caregiver burden due to RSV illness in the current population. This will allow the determination of social and economic resources that are required for infants who have LRTI. Serum anti-RSV neutralizing antibody levels will be evaluated for correlation with serum MEDI8897 and palivizumab concentrations. RSV serology will be evaluated to identify potential exposure to RSV. To monitor for RSV resistance, the F protein from collected RSV isolates will be genetically characterized and novel variants will be phenotypically characterized for MEDI8897 and palivizumab susceptibility. The incidence of medically attended LRTI (inpatient and outpatient) due to RT-PCR-confirmed RSV from Day 152 to Day 361 in Season 1 and Season 2 will be assessed to determine if there is a possible effect of MEDI8897 past Day 151.

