ADA = anti-drug antibody; AEs = adverse events; AESIs = adverse events of special interest; CHD = congenital heart disease; CLD = chronic lung disease; D = study day; ER = emergency room; HRU = healthcare resource utilization; ICU = intensive care unit; IM=intramuscular; LRTI = lower respiratory tract infection; neut Ab = neutralizing antibody; NOCDs = new onset chronic diseases; OTC = over-the-counter; PK = pharmacokinetic; Q2W = once every 2 weeks; RSV = respiratory syncytial virus; SAEs = serious adverse events; SID = subject identification; TC = telephone call; V = visit.

^a Visit 2/Day 1 and Visit 1/Screening can occur on the same day.

^b For subjects in the CLD/CHD cohort, the Season 1 Visit 9/Day 361 may be the same as the Season 2 Visit 10/Day 1 (Dose 1).

^c All vital signs (temperature, blood pressure, heart rate, and respiratory rate) should be obtained within 60 minutes prior to dosing, and at 30 minutes (± 5 minutes) and 60 minutes (± 5 minutes) post dose.

^d Subjects requiring a replacement dose of study drug due to cardiac surgery with cardiopulmonary bypass will have a blood sample collected before and after surgery (prior to administering replacement dose) for PK evaluation.

^e If Visit 1/Screening and Visit 2/Day 1 do not occur on the same day, blood sample for PK, ADA, RSV neut Ab, and RSV serology can be collected at either Visit 1/Screening or Visit 2/Day 1 predose.

^f Nasal samples will be collected from all subjects with LRTIs (inpatient or outpatient) and from all hospitalized subjects with any new respiratory infection (upper or lower) within approximately 2 days after the initial healthcare provider assessment and diagnosis.

Blood samples will be collected from all subjects hospitalized with LRTI or any respiratory infection within approximately 2 days following hospital admission.

^g Subjects in each cohort (preterm and CLD/CHD cohorts) will be randomized 2:1 to receive either MEDI8897 administered as a stratified dose by weight band, which includes a single fixed 50-mg IM dose for infants weighing < 5 kg or 100-mg IM dose for infants weighing ≥ 5 kg, followed by 4 once-monthly IM doses of placebo; or 5 once-monthly IM doses of 15 mg/kg palivizumab.

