- Gender
- Race (Caucasian, non-Caucasian)
- Weight at birth (weight ≤ 2.5 kg, weight ≥ 2.5 kg)
- Weight on Day 1 (weight $\leq 5 \text{ kg}$, weight $\geq 5 \text{ kg}$)
- GA (< 29 weeks, ≥ 29 weeks to < 32 weeks, ≥ 32 weeks to < 35 weeks, ≥ 35 weeks)
- Sibling also participating in the study (yes/no)

In addition, the incidence of medically attended RSV LRTI that occurred through 360 days post 1st dose will be summarized by treatment group.

Age at onset of the first medically attended RSV LRTI through 150 days post 1st dose will be tabulated by age group used for randomization stratification by treatment group. In addition, time-to-first medically attended RSV LRTI will be plotted at subject's level along the axis of age at birth.

The incidence of medically attended RSV LRTI by subtype (RSV A, RSV B) through 150 days post 1st dose, through 360 days post 1st dose will be summarized by treatment group.

To capture and summarize multiple medically attended RSV LRTIs through 150 days post 1st dose, the total number of new onset medically attended RSV LRTIs will be calculated for each subject. A new onset medically attended RSV LRTI is defined as an adverse event (AE) meeting the protocol specified criteria for a medically attended RSV LRTI and occurring at least 14 days after the resolution date of the previous AE for a medically attended RSV LRTI. A similar definition is applied with a 30-day interval between the resolution of the previous

event and onset of a new event (see Table 2 for details). A listing will be generated to provide the following information: age at randomization, hemisphere, total number of events (at least 14 days apart), total number of events (at least 30 days apart), days to event, adverse event (AE) verbatim term, date of AE onset/stop, days from previous event, visit setting, and RSV subtype.

AEs associated with medically attended RSV LRTI will be summarized overall, as well as categorized by MedDRA system organ class (SOC) and preferred term (PT). Summaries will be presented through 150 days post 1st dose, and through 360 days post 1st dose.

Above summaries will be repeated for each cohort (pre-term and CHD/CLD).

3.5.1.2 Analysis of incidence of medically attended LRTI due to RT-PCR-confirmed RSV in Season 2

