3.7 Safety Analyses

All safety analyses will be conducted on as-treated population.

For each season as well as the two consecutive seasons combined (ie, Season 1, Season 2, Season 1 + Season 2) the summaries will be provided using the respective as-treated population. The Season 1 summaries will also be provided for each cohort (pre-term, CHD/CLD).

For each season, all safety analyses planned will be presented. For Season 1 + Season 2, number and percentage of subjects with treatment-emergent adverse events (TEAEs), treatment-emergent serious adverse events (TESAEs), adverse events of special interest (AESIs), IP-related skin reactions, and new onset chronic diseases (NOCDs) will be summarized by MedDRA System Organ Class (SOC) and Preterm Term (PT) for palivizumab/palivizumab and MEDI88987/MEDI8897 groups. The Season 1 + Season 2 summaries will be presented for CLD/CHD cohort, for CLD subjects and CHD subjects, separately.

For Season 2 summaries and Season 1 + Season 2 summaries, direct comparison between MEDI8897/MEDI8897 with palivizumab/palivizumab groups are subject to potential bias if the dropouts of Season 1 are associated with safety.

 Table 3
 Reporting Period of Treatment-emergent Adverse Events

Reporting Period	Definition of Treatment-emergent AEs	
Season 1	Any AEs that started on/after date of 1 st dose of Season 1, and prior to the end of Season 1, Day 361 or the last day prior to 1 st dose of Season 2, whichever comes earlier.	
Season 2	Any AEs that started on/after date of 1st dose of Season 2 and prior to the end of Season 2, Day 361.	
Season 1 + Season 2	Any AEs that started on/after date of 1st dose of Season 1 and prior to the end of Season 2, Day 361.	

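### Season 1 late efficacy, HRU and caregiver windows do not stop at Season 2 Dose 1, so an RSV LRTI in a short overlap can be counted under both seasons

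*SAP*

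**What the plan says.** **Season 1 late window.** SAP 3.6.6 counts "medically attended RSV LRTI that occurred > 150 days (from Day 152 to Day 361) post 1st dose", by treatment group and by cohort, including CHD/CLD. The population is "subjects from the respective ITT population who remained in the study at the Day 151 visit". For a child with several events, "only the first occurrence will be used in the summary". SAP 3.5.1.1 adds that "the incidence of medically attended RSV LRTI that occurred through 360 days post 1st dose will be summarized by treatment group". SAP 3.5.3, 3.6.1 and 3.6.2 use the same after-150-day and through-360-day periods for all LRTI, HRU and caregiver burden. None of these sections mentions Season 2 dosing as an end point for Season 1.

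**Season 2 window.** SAP 3.5.1.2 starts the Season 2 efficacy summary on Season 2 Day 1, the day of Season 2 Dose 1.

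**Timing of the two visits.** Protocol Table 5, footnote b, says that for the CLD/CHD cohort "the Season 1 Visit 9/Day 361 may be the same as the Season 2 Visit 10/Day 1 (Dose 1". The same table gives Day 361 a window of ±7 days.

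**Safety.** SAP Table 3 ends the Season 1 TEAE period "prior to the end of Season 1, Day 361 or the last day prior to" the first Season 2 dose, taking the earlier of the two dates.

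**Purpose.** Protocol 3.2.3 says that the Day 152 to Day 361 incidence is assessed "to determine if there is a possible effect of MEDI8897 past Day 151".

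**The concern.** The SAP foresaw for adverse events that Season 2 dosing can precede the end of Season 1, and it wrote a rule. It wrote none for efficacy, HRU or caregiver burden.

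Two things follow for a CLD/CHD child dosed for Season 2 on or before Season 1 Day 361. First, an RSV LRTI after that dose satisfies both seasons' definitions. The first-occurrence rule works within one season's summary and does not prevent this. Second, the efficacy and safety tables disagree. SAP 3.6.6 tabulates the adverse events linked to late Season 1 RSV LRTI, yet Table 3 makes the same adverse event a Season 2 TEAE only.

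At stake is what the late Season 1 result means. It is meant to show whether the Season 1 dose still has an effect after Day 151. Time after a further dose, or after a switch from palivizumab to MEDI8897, cannot show that.

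**Working it through.** **Inputs**
- Day 1 is the first dosing day (Protocol 4.5.1.2), so Day d is d − 1 days post dose.
- Day 361 visit window: ±7 days; the visit may coincide with Season 2 Dose 1 (Protocol Table 5).
- CLD/CHD cohort: about 300 of 900 children. In Season 2 about 200 are MEDI8897/MEDI8897, 50 palivizumab/MEDI8897 and 50 palivizumab/palivizumab (Protocol 3.1.1).
- RSV LRTI rate: 6% (Protocol 4.8.2), used only to size the overlap.

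**The plan's own window.** More than 150 and up to 360 days post dose is Day 152 to Day 361. Its length is 361 − 152 + 1 = 210 days. The stated limits reproduce.

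**Overlap.** If Season 2 Dose 1 falls on Season 1 Day s, with s ≤ 361, the overlap is 361 − s + 1 days. The earliest on-schedule day is 361 − 7 = 354.

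| Season 2 Dose 1 on Season 1 day | Overlap | Share of 210 days | Late window after a Table 3 cut |
|---|---|---|---|
| 361 | 1 day | 0.5% | Day 152–360, 209 days |
| 354 | 8 days | 3.8% | Day 152–353, 202 days |

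If Season 2 Dose 1 comes after Day 361, there is no overlap.

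**Share of the whole Season 1 late summary**, if every CLD/CHD child were dosed on Day 354 and all were followed throughout:
- All children: 8 × 300 / (210 × 900) = 1.3% of late person-time.
- Switchers within the palivizumab group: 8 × 50 / (210 × 300) = 0.6%.

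**Events that could be counted twice.** Assume the rate is spread evenly over the 151 days from Day 1 to Day 151, and that all are dosed on Day 354:
- 300 children at 6%: 300 × 0.06 × 8/151 = 0.95.
- 50 switchers at 6%: 50 × 0.06 × 8/151 = 0.16.
- 300 children at an assumed 1%: 300 × 0.01 × 8/151 = 0.16. A lower rate is shown because Protocol 4.8.2 warns that pandemic measures may reduce events.

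**One case traced through.** A palivizumab/MEDI8897 child has Season 2 Dose 1 on Season 1 Day 354 and an RSV LRTI on Day 358, which is Season 2 Day 358 − 354 + 1 = 5. The illness is:
- in the Season 1 late summary, under palivizumab;
- in the Season 2 through-150-days summary, under palivizumab/MEDI8897;
- a TEAE in Season 2 only.

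**The case against.** **The overlap is short.** The notes to Protocol Figure 1 place the CLD/CHD Day 361 blood sample before Season 2 dosing, and Season 2 has no Day 1 blood draw. SAP 3.7.1 also provides for adverse events falling after Season 1 Day 361 and before Season 2 Day 1, so a gap between seasons is expected for some children. The coinciding visit alone explains why Table 3 has its cut. This stands. A reader might infer that Season 2 dosing follows the epidemic calendar and could come weeks early, at a time when RSV is most frequent. The documents do not support that. They give no date before Day 354, although they state no minimum interval either, and they do not say when within a season events are likeliest.

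**No reported total is inflated.** The current SAP has no combined two-season efficacy, HRU or caregiver summary. This also stands. A reader might infer that the Season 2 secondary endpoint or the primary efficacy endpoint is corrupted. Neither is: the event belongs in Season 2 and is correctly counted there, and the primary efficacy endpoint ends at 150 days.

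**The outputs are low-stakes.** The Day 152 to Day 361 endpoint, HRU and caregiver burden are exploratory, the through-360-day LRTI tables are supplementary, and no hypothesis is tested. True, and it limits the priority.

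**A fixed window by randomised group is a legitimate intent-to-treat summary with equal scheduled follow-up.** It is, but it answers a different question from the one in Protocol 3.2.3, and it leaves the disagreement with Table 3 in place. The point about equal follow-up stands and must be met in the fix.

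**Vendors split data by season.** Protocol 4.8.1 and SAP 3.1 do this to protect the blind at the primary lock. It is not a rule for counting events.

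**Conclusion.** The inconsistency is real and small. As written, the Season 1 late and through-360-day summaries can include RSV LRTI that occurred on or after Season 2 Dose 1, and the Season 2 summary counts the same illness. The effect is confined to the CLD/CHD cohort, because preterm children have no Season 2. The drug is wrongly attributed only for the roughly 50 switchers; the other CLD/CHD children keep the same drug but have started a new course.

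The size rests on Season 2 Dose 1 being given on schedule. On that basis at most about one double-counted event is expected, even with all 300 children dosed on Day 354 and a 6% rate. Dosing before Day 354 would add one day of overlap per day earlier, but the documents give no basis for a figure. With few events expected in Season 2 groups of about 50, a single event can still be visible in a table, so the rule should be set before those tables are produced.

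**What to change.** In SAP 3.5.1.1, 3.5.3, 3.6.1, 3.6.2 and 3.6.6, end the Season 1 after-150-day and through-360-day windows at the earlier of Day 361 and the day before Season 2 Dose 1, as Table 3 does. State that an event on or after Season 2 Dose 1 belongs to Season 2 only.

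The cut date is already needed for Table 3, so programming is light. The cost is that late follow-up becomes slightly shorter and unequal for some CLD/CHD children: 202 to 209 days instead of 210 when Season 2 Dose 1 falls on Days 354 to 361. Because SAP 3.5 defines incidence as a simple proportion, report time at risk, or the number of children with a shortened window, by group beside the proportions.

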3.7 Safety Analyses

All safety analyses will be conducted on as-treated population.

For each season as well as the two consecutive seasons combined (ie, Season 1, Season 2, Season 1 + Season 2) the summaries will be provided using the respective as-treated population. The Season 1 summaries will also be provided for each cohort (pre-term, CHD/CLD).

For each season, all safety analyses planned will be presented. For Season 1 + Season 2, number and percentage of subjects with treatment-emergent adverse events (TEAEs), treatment-emergent serious adverse events (TESAEs), adverse events of special interest (AESIs), IP-related skin reactions, and new onset chronic diseases (NOCDs) will be summarized by MedDRA System Organ Class (SOC) and Preterm Term (PT) for palivizumab/palivizumab and MEDI88987/MEDI8897 groups. The Season 1 + Season 2 summaries will be presented for CLD/CHD cohort, for CLD subjects and CHD subjects, separately.

For Season 2 summaries and Season 1 + Season 2 summaries, direct comparison between MEDI8897/MEDI8897 with palivizumab/palivizumab groups are subject to potential bias if the dropouts of Season 1 are associated with safety.

 Table 3
 Reporting Period of Treatment-emergent Adverse Events

Reporting Period	Definition of Treatment-emergent AEs	
Season 1	Any AEs that started on/after date of 1 st dose of Season 1, and prior to the end of Season 1, Day 361 or the last day prior to 1 st dose of Season 2, whichever comes earlier.	
Season 2	Any AEs that started on/after date of 1st dose of Season 2 and prior to the end of Season 2, Day 361.	
Season 1 + Season 2	Any AEs that started on/after date of 1st dose of Season 1 and prior to the end of Season 2, Day 361.	

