RSV resistance monitoring	To characterize resistance to MEDI8897 and palivizumab through genotypic and phenotypic analyses	Genotypic analysis and susceptibility of RSV variants to neutralization by MEDI8897 and palivizumab
RSV LRTI after Day 151	To assess the incidence of medically attended LRTI due to RT-PCR-confirmed RSV, compared to palivizumab after Day 151	Incidence of medically attended LRTI (inpatient and outpatient) due to RT-PCR-confirmed RSV from Day 152 to Day 361 for Season 1 and Season 2

AbU/mL = antibody unit per mL; ADA = anti-drug antibody; AESI = adverse event of special interest; AUC = area under the concentration-time curve; CHD = congenital heart disease; CLD = chronic lung disease; C_{max} = maximum observed concentration; ER = emergency room; GMFR = geometric mean fold-rise; GMT = geometric mean titer; HRU = healthcare resource utilization; ICU = intensive care unit; IM = intramuscular; LRTI = lower respiratory tract infection; NOCD = new onset chronic disease; OTC = over-the-counter; PK = pharmacokinetic; RSV = respiratory syncytial virus; RT-PCR = reverse transcriptase-polymerase chain reaction; t_{1/2} = terminal half-life; TEAE = treatment-emergent adverse event; TESAE = treatment-emergent serious adverse event.
		

STUDY DESIGN

Study D5290C00005 (MEDLEY) is a pivotal Phase 2/3 randomized, double-blind, palivizumab-controlled study to evaluate the safety, PK, ADA response, and descriptive efficacy for MEDI8897 in high-risk infants eligible to receive palivizumab when entering their first or second RSV season (Season 1 or Season 2, respectively). Approximately 900 palivizumab-eligible infants entering their first RSV season will be enrolled into one of 2 cohorts: (1) preterm cohort, including approximately 600 preterm infants (≤ 35 weeks gestational age [GA]) without CLD/CHD, or (2) CLD/CHD cohort, including approximately 300 infants with CLD of prematurity or hemodynamically significant CHD. A minimum of 100 infants with hemodynamically significant CHD will be enrolled. Within each cohort, randomization will be stratified by hemisphere (northern, southern) and subject age at the time of Season 1 randomization (≤ 3 months, > 3 to ≤ 6 months, > 6 months).

Season 1, Preterm and CLD/CHD Cohorts

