All subjects will be randomized 2:1 to either the MEDI8897 group (approximately 600 subjects, including approximately 400 subjects in the preterm cohort and approximately 200 subjects in the CLD/CHD cohort) or palivizumab group (approximately 300 subjects, including approximately 200 subjects in the preterm cohort and approximately 100 subjects in the CLD/CHD cohort). Subjects in the MEDI8897 group will receive a single fixed IM dose of MEDI8897 followed by 4 once-monthly IM doses of placebo. The MEDI8897 dose level will be stratified by weight band, ie, 50 mg for infants weighing < 5 kg or 100 mg for infants weighing ≥ 5 kg. Subjects in the palivizumab group will receive 5 once-monthly IM doses of 15 mg/kg palivizumab.

Season 2, CLD/CHD Cohort Only

- Subjects with CLD/CHD ≤ 24 months of age who were randomized to the MEDI8897 group for Season 1 will receive a single fixed IM dose of 200 mg MEDI8897 followed by 4 once-monthly IM doses of placebo (approximately 200 subjects).
- Subjects with CLD/CHD ≤ 24 months of age who were randomized to the palivizumab group for Season 1 will be re-randomized 1:1 to either the MEDI8897 group or the palivizumab group. Subjects in the MEDI8897 group will receive a single fixed IM dose of 200 mg MEDI8897 followed by 4 once-monthly IM doses of placebo (approximately 50 subjects). Subjects in the palivizumab group will receive 5 once-monthly IM doses of 15 mg/kg palivizumab (approximately 50 subjects).

In Season 1 or Season 2, subjects in the CLD/CHD cohort who undergo cardiac surgery with cardiopulmonary bypass after receipt of Dose 1 but prior to receipt of Dose 5 will receive a replacement dose of the study drug they received for Dose 1 immediately following the surgery when determined by the physician to be medically stable for an IM injection. Any subsequent doses of study drug will continue to be given according to the protocol-specified dosing schedule.

Subjects in the preterm cohort will be followed through 1 year after Season 1/Dose 1, and subjects in the CLD/CHD cohort will be followed through 1 year after Season 2/Dose 1. Subjects in the CLD/CHD cohort who receive a replacement dose in Season 2 will be followed through 1 year after the last replacement dose.

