4.8.3 Safety

4.8.3.1 Analysis of Adverse Events

AEs will be graded according to the current version of the NCI CTCAE where applicable for pediatric assessments. AEs will be coded by the Medical Dictionary for Regulatory Activities and the type, incidence, severity, and relationship to study drug will be summarized by treatment group. Other safety assessments will include the occurrence of AESIs defined as AEs of hypersensitivity to study drug (including anaphylaxis), thrombocytopenia, and immune complex disease (eg, vasculitis, endocarditis, neuritis, glomerulonephritis) following study drug administration, and the occurrence of NOCDs following study drug administration.

Safety of MEDI8897 will be summarized by treatment group based on the ATP. The safety summary will be provided for each season, as well as for the 2 consecutive RSV seasons (ie, Season 1 and Season 2). For the Season 1 summary, the analysis dataset will include subjects from the preterm cohort and CLD/CHD cohort, presented by the treatment received in Season 1; for the Season 2 summary and the 2 consecutive-season summary, the analysis dataset will include subjects from the CLD/CHD cohort, presented by the treatment received through the 2 seasons.

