2.3 Treatment Assignment and Blinding

2.3.1 Methods for Assigning Treatment Groups

An IWRS will be used for randomization to a treatment group and assignment of blinded investigational product kit numbers. A subject is considered randomized into the study when the investigator notifies the IWRS that the subject meets eligibility criteria and the IWRS provides the assignment of blinded investigational product kit numbers to the subject.

In Season 1, subjects in the preterm and CLD/CHD cohorts will be randomized using a 2:1 ratio to either the MEDI8897 group or palivizumab group. Within each cohort, the randomization will be stratified by hemisphere (northern, southern) and subject age at the time of Season 1 randomization ($\leq 3.0 \text{ months}$, $> 3.0 \text{ to} \leq 6.0 \text{ months}$, > 6.0 months).

In Season 2, subjects in the CLD/CHD cohort only will be randomized. Subjects who were randomized to the MEDI8897 group in Season 1 will remain in the MEDI8897 group. Subjects who were randomized to the palivizumab group in Season 1 will be re-randomized using a 1:1 ratio to either the MEDI8897 or palivizumab group. For simplicity, the following notations will be used to describe the treatment groups in Season 2.

- MEDI8897/MEDI8897: CHD/CLD subjects who were randomized to MEDI8897 group in Season 1 and remained in MEDI8897 group in Season 2.
- Palivizumab/MEDI8897: CHD/CLD subjects who were randomized to Palivizumab group in Season 1 and re-randomized to MEDI8897 group in Season 2.
- Palivizumab/Palivizumab: CHD/CLD subjects who were randomized to Palivizumab group in Season 1 and re-randomized to Palivizumab group in Season 2.

Study drug (MEDI8897, placebo, or palivizumab) must be administered the same day the study drug is assigned. If there is a delay in the administration of study drug such that it will not be administered within the specified timeframe, the unblinded investigational product monitor must be notified immediately.

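### SAP 3.7 leaves the palivizumab/MEDI8897 sequence out of the five Season 1 + Season 2 safety event summaries, although Protocol 4.8.3.1 excludes no sequence and SAP Table 1 counts these children in the population

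*SAP*

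**What the plan says.** Protocol 4.8.3.1 (repeated in the synopsis, under Safety) asks for a safety summary for each season and for both seasons together. For "the 2 consecutive-season summary, the analysis dataset will include subjects from the CLD/CHD cohort, presented by the treatment received through the 2 seasons". It lists no groups and excludes none.

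The design yields three sequences. SAP 2.3.1 names all of them, including the switched group: "Palivizumab/MEDI8897: CHD/CLD subjects who were randomized to Palivizumab group in Season 1 and re-randomized to MEDI8897 group in Season 2".

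SAP Table 1 defines the as-treated population (Season 2) as subjects who receive any investigational product in that season, and makes it the population for safety in Season 2 and over both seasons. The switched group is in it.

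SAP 3.7 then plans every safety analysis for each single season. For Season 1 + Season 2 it plans five summaries by SOC and PT (TEAEs, TESAEs, AESIs, IP-related skin reactions, NOCDs) "for palivizumab/palivizumab and MEDI88987/MEDI8897 groups". The same paragraph says these are presented for the CLD/CHD cohort and for CLD and CHD subjects separately. It adds a caution that "direct comparison between MEDI8897/MEDI8897 with palivizumab/palivizumab groups are subject to potential bias if the dropouts of Season 1 are associated with safety".

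**The concern.** Safety is the primary objective. Four of the five summaries (TEAEs, TESAEs, AESIs, NOCDs) are the components of the primary endpoint in Protocol Table 1. The protocol's rule gives three columns and the SAP gives two. The missing group is the only one assigned both antibodies in sequence.

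The SAP does not explain the omission. Its amendment history gives possible dropout bias between MEDI8897/MEDI8897 and palivizumab/palivizumab as the reason for repeating only a few key summaries over two seasons. That is a reason for fewer tables, not for removing the third group. For ADA, where SAP 3.8 also leaves the switched group out of the two-season summary, the amendment history does give a reason: these children first receive MEDI8897 in Season 2. Safety has no counterpart to that.

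At stake is a complete two-season tabulation. Without the column, no planned table shows how many switched children had a given event at any time over the two seasons.

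**Working it through.** **1. Reproduce the planned size of the group.** Inputs from the protocol synopsis (Study Design):

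- cohort size: "CLD/CHD cohort, including approximately 300 infants with CLD of prematurity or hemodynamically significant CHD"
- Season 1 allocation: "All subjects will be randomized 2:1 to either the MEDI8897 group"
- Season 2: subjects "randomized to the palivizumab group for Season 1 will be re-randomized 1:1 to either the MEDI8897 group or the palivizumab group"

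Season 1 palivizumab = 300 × 1/3 = 100. Switched = 100 × 1/2 = 50. This matches the protocol's own figure of approximately 50. The other sequences are 300 × 2/3 = 200 (MEDI8897/MEDI8897) and 50 (palivizumab/palivizumab).

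**2. Size of the omission.**

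| Quantity | Calculation | Result |
|---|---|---|
| Children in the two-season event tables, SAP 3.7 | 200 + 50 | 250 |
| Children under Protocol 4.8.3.1 | 200 + 50 + 50 | 300 |
| Share of cohort omitted | 50/300 | 16.7% |
| Share of Season 2 MEDI8897 recipients omitted | 50/(200 + 50) | 20% |

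These figures assume that no child is lost before Season 2. The documents give no attrition rate. At assumed losses of 10%, 20% and 30%, the omitted number is 50 × 0.9 = 45, 50 × 0.8 = 40 and 50 × 0.7 = 35. The share stays at 16.7% if loss is equal across sequences.

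**3. Chance that the omitted group contains an event.** With n = 50, the probability that at least one child is affected is 1 − (1 − p)^50. At assumed true rates p of 0.5%, 1% and 2% this is 22.2%, 39.5% and 63.6%. The 0.5% rate is the one used in the plan's sample-size statement. These rates are illustrations, not forecasts.

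**4. Can the single-season tables supply the missing count?** Not exactly.

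- In the Season 1 tables the switched children sit in the palivizumab column. Even in the CLD/CHD cohort table (planned 100) they are mixed with children later assigned palivizumab again and with any who never enter Season 2. Their own Season 1 count is not shown.
- SAP 3.7.1 counts a given AE once per subject within a summary. If *a* switched children had an event in Season 1 and *b* in Season 2, the number affected within those two windows lies anywhere from max(*a*, *b*) to *a* + *b* (capped at the group size).

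**5. Events between the seasons.** By SAP Table 3, the Season 1 window ends at Season 1 Day 361 or the day before Season 2 Dose 1, whichever is earlier, and the Season 2 window opens at Season 2 Dose 1. An event in between belongs to neither. SAP 3.7.1 sends it to listings. The Season 1 + Season 2 window in Table 3 runs without a break and would include it. Under Table 3 such an event can therefore be tabulated for the two named groups but not for the switched group.

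Two limits apply. The gap exists only where the two visits differ, and the protocol's schedule tables allow them to coincide. Also, the listing rule in 3.7.1 does not say which reporting period it governs.

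**The case against.** The case for leaving the SAP as it stands has several sound parts.

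- **Little is hidden.** Apart from events between the seasons, which are listed, each switched child's events are tabulated: Season 1 under palivizumab, Season 2 under palivizumab/MEDI8897. The final analysis includes all data. A reader might infer that these children have no cumulative safety record. The documents do not support that; what is missing is a per-child two-season count in a table.
- **The omission is narrower than it may look.** A reader might infer that the group is absent from all two-season output. It is not. The exposure summary in SAP 3.4.3 covers everyone enrolled in Season 2, and the neutralizing-antibody and serology summaries (SAP 3.6.3, 3.6.4) carry no group restriction.
- **The randomised comparison is not lost.** A reader might infer that the SAP keeps the comparison open to dropout bias and discards the protected one. But re-randomisation takes place at Season 2 Day 1, so palivizumab/MEDI8897 versus palivizumab/palivizumab belongs to the Season 2 period, where every planned safety analysis is presented. A two-season table would only add events from a season in which both groups received palivizumab.
- **The column is of mixed exposure.** Showing two-season incidence only for children kept on one antibody is a defensible choice, and splitting the column at Season 2 Dose 1 partly repeats the season tables.
- **The protocol does not list the groups here**, as it does for efficacy in 4.8.4.

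The first three points stand and limit the finding. The fourth would be a fair reason if the SAP gave it, but it does not. The fifth is weak: presentation by treatment received through two seasons, on a cohort with three planned sequences and no exclusion, most naturally means three groups.

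**Conclusion.** SAP 3.7 departs without explanation from Protocol 4.8.3.1 and does not fit its own Table 1. The departure affects five two-season event summaries, four of which carry the primary-endpoint components. On planned numbers about 50 of 300 CLD/CHD children (16.7%) are left out of those summaries, with the attrition caveat shown above.

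The loss is a tabulated two-season count per child, plus tabulation of any event between Season 1 Day 361 and Season 2 Day 1 if Table 3 governs that interval. The study is descriptive, so no test or formal conclusion changes. This is a correction worth making because it concerns the primary objective and costs little, not a flaw that threatens the trial's interpretation.

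**What to change.** In SAP 3.7, plan the Season 1 + Season 2 summaries for three columns: MEDI8897/MEDI8897, palivizumab/MEDI8897 and palivizumab/palivizumab. In the switched column, count each child once in the total and show events by onset before or after Season 2 Dose 1, so that palivizumab-period events are not read as MEDI8897 events. State that the Season 1 + Season 2 window of Table 3 applies to all three columns, so that between-season events are treated alike.

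No new named contrast is needed, because the Season 2 tables already carry the re-randomised comparison.

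The cost is a wording change and one extra column with a split in five summaries, for a small group of mixed exposure. No extra data are collected and the sample size is unaffected. If the sponsor prefers two columns, the SAP should record this as a departure from Protocol 4.8.3.1 and give the reason.
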